## 2.1.1 Baseline Documentation of ‘Target’ and ‘non-target’ Lesions

Where more than one measurable lesion is present at baseline all lesions up to a maximum of five lesions total (and a maximum of two lesions per organ) representative of all involved organs should be identified as *target lesions* and will be recorded and measured at baseline. For example, in instances where patients have only one or two organ sites involved, a maximum of two and four lesions respectively will be recorded). Target lesions should be selected on the basis of their size (lesions with the longest diameter), be representative of all involved organs, but in addition should be those that lend themselves to *reproducible repeated measurements*. It may be the case that, on occasion, the largest lesion does not lend itself to reproducible measurement in which circumstance the next largest lesions which can be measured reproducibly should be selected.

*Lymph nodes* merit special mention since they are normal anatomical structures which may be visible by imaging even if not involved by tumor. As noted above, pathological nodes which are defined as measurable and may be identified as target lesions must meet criterion of a short axis of  $\geq 15$  mm by CT scan. Only the *short* axis of these nodes will contribute to the baseline sum. The short axis of the node is the diameter normally used by radiologists to judge if a node is involved by solid tumor. Nodal size is normally reported as two dimensions in the plane in which the image is obtained (for CT scan this is almost always the axial plane; for MRI the plane of acquisition may be axial, sagittal or coronal). The smaller of these measures is the short axis. For example, an abdominal node which is reported as being 20 mm x30 mm has a short axis of 20 mm and qualifies as a malignant, measurable node. In this example, 20 mm should be recorded as the node measurement. All other pathological nodes (those with short axis  $\geq 10$  mm but  $< 15$  mm) should be considered non-target lesions. Nodes that have a short axis  $< 10$  mm are considered non-pathological and should not be recorded or followed.

A *sum of the diameters* (longest for non-nodal lesions, short axis for nodal lesions) for all target lesions will be calculated and reported as the *baseline sum diameters*. If lymph nodes are to be included in the sum, then as noted above, only the *short* axis is added into the sum. The baseline sum diameters will be used as reference to further characterize any objective tumor regression in the measurable dimension of the disease.

All other lesions (or sites of disease) including pathological lymph nodes should be identified as *non-target lesions* and should also be recorded at baseline. Measurements are not required and these lesions should be followed as ‘present’, ‘absent’, or in rare cases ‘unequivocal progression. In addition, it is possible to record multiple non-target lesions involving the same organ as a single item on the case record form (e.g. ‘multiple enlarged pelvic lymph nodes’ or ‘multiple liver metastases’).

## 2.2 Response Criteria

This section provides the definitions of the criteria used to determine objective tumor response for target lesions.

## 2.2.1 Evaluation of Target Lesions

*Complete Response (CR)*: Disappearance of all target lesions. Any pathological lymph nodes (whether target or non-target) must have reduction in short axis to  $< 10$  mm.

*Partial Response (PR)*: at least a 30% decrease in the sum of diameters of target lesions, taking as reference the baseline sum diameters.

*Progressive Disease (PD)*: at least a 20% increase in the sum of diameters of target lesions, taking as reference the *smallest sum on study* (this includes the baseline sum if that is the smallest on study). In addition to the relative increase of 20%, the sum must also demonstrate an absolute increase of at least 5 mm. (*Note*: the appearance of one or more new lesions is also considered progression).

*Stable Disease (SD)*: Neither sufficient shrinkage to qualify for PR nor sufficient increase to qualify for PD, taking as reference the smallest sum diameters while on study.

## 2.2.2 Special Notes on the Assessment of Target Lesions

*Lymph nodes*. Lymph nodes identified as target lesions should always have the actual short axis measurement recorded (measured in the same anatomical plane as the baseline examination), even if the nodes regress to below 10 mm on study. This means that when lymph nodes are included as target lesions, the ‘sum’ of lesions may not be zero even if complete response criteria are met, since a normal lymph node is defined as having a short axis of  $< 10$  mm. In order to qualify for CR, each node must achieve a short axis  $< 10$  mm. For PR, SD and PD, the actual short axis measurement of the nodes is to be included in the sum of target lesions.

*Target lesions that become ‘too small to measure’*. While on study, all lesions (nodal and non-nodal) recorded at baseline should have their actual measurements recorded at each subsequent evaluation, even when very small (e.g. 2 mm). However, sometimes lesions or lymph nodes which are recorded as target lesions at baseline become so faint on CT scan that the radiologist may not feel comfortable assigning an exact measure and may report them as being ‘too small to measure’. When this occurs, it is important that a value be recorded on the case report form. If it is the opinion of the radiologist that the lesion has likely disappeared, the measurement should be recorded as 0 mm. If the lesion is believed to be present and is faintly seen but too small to measure, a default value of 5 mm should be assigned (*Note*: It is less likely that this rule will be used for lymph nodes since they usually have a definable size when normal and are frequently surrounded by fat such as in the retroperitoneum; however, if a lymph node is believed to be present and is faintly seen but too small to measure, a default value of 5 mm should be assigned in this circumstance as well). This default value is derived from the 5 mm CT slice thickness (but should not be changed with varying CT slice thickness). The measurement of these lesions is potentially non-reproducible, therefore providing this default value will prevent false responses or progressions based upon measurement error. However, if the radiologist is able to provide an actual measure, that should be recorded, even if it is below 5 mm.

*Lesions that split or coalesce on treatment.* When non-nodal lesions ‘fragment’, the longest diameters of the fragmented portions should be added together to calculate the target lesion sum. Similarly, as lesions coalesce, a plane between them may be maintained that would aid in obtaining maximal diameter measurements of each individual lesions. If the lesions have truly coalesced such that they are no longer separable, the vector of the longest diameter in this instance should be the maximal longest diameter for the ‘coalesced lesion’.

### **2.2.3 Evaluation of Nontarget Lesions**

This section provides the definitions of the criteria used to determine the tumor response for the group of non-target lesions. While some non-target lesions may actually be measurable, they need not be measured and instead should be assessed only *qualitatively* at the time points specified in the protocol.

*Complete Response (CR):* Disappearance of all nontarget lesions. All lymph nodes must be non-pathological in size (< 10 mm short axis).

*Non-CR/Non-PD:* Persistence of one or more nontarget lesions(s).

*Progressive Disease (PD): Unequivocal progression* (see comments below) of existing non-target lesions. (*Note:* the appearance of one or more new lesions is also considered progression).

### **2.2.4 Special Notes on Assessment of Progression of Nontarget Disease**

The concept of progression of nontarget disease requires additional explanation as follows:

*When a patient also has measurable disease.* In this setting, to achieve ‘unequivocal progression; on the basis of the non-target disease, there must be an overall level of substantial worsening in non-target disease such that, even in presence of SD or PR in target disease, the overall tumor burden has increased sufficiently to merit discontinuation of therapy. A modest ‘increase’ in the size of one or more non-target lesions is usually not sufficient to qualify for unequivocal progression status. The designation of overall progression *solely* on the basis of change in non-target disease in the face of SD or PR of target disease will therefore be extremely rare.

*When the patient has only non-measurable disease.* The same general concepts apply here as noted above, *however*, in this instance there is no measurable disease assessment to factor into the interpretation of an increase in non-measurable disease burden. Because worsening in non-target disease cannot be easily quantified (by definition: if all lesions are truly non-measurable) a useful test that can be applied when assessing patients for unequivocal progression is to consider if the increase in overall disease burden based on the change in non-measurable disease is comparable in magnitude to the increase that would be required to declare PD for measurable disease: i.e. an increase in tumor burden representing an additional 73% increase in ‘volume’ (which is equivalent to a 20% increase diameter in a measurable lesion). Examples include an increase in a pleural effusion from ‘trace’ to ‘large’, an increase in lymphangitic disease from localized to widespread, or may be described in protocols as ‘sufficient to require a change in therapy’. If ‘unequivocal progression’ is seen, the patient should be considered to have had

overall PD at that point. While it would be ideal to have objective criteria to apply to non-measurable disease, the very nature of that disease makes it impossible to do so; therefore, the increase must be substantial.

### **2.2.5 New Lesions**

The appearance of new malignant lesions denotes disease progression. There are no specific criteria for the identification of new radiographic lesions; however, the finding of a new lesion should be unequivocal: i.e. not attributable to differences in scanning technique, change in imaging modality or findings thought to represent something other than tumor (for example, some 'new' bone lesions may be simply healing or flare of pre-existing lesions). This is particularly important when the patient's baseline lesions show partial or complete response. For example, necrosis of a liver lesion may be reported on a CT scan report as a 'new' cystic lesion, which it is not.

A lesion identified on a follow-up study in an anatomical location that was *not* scanned at baseline is considered a new lesion and will indicate disease progression. An example of this is the patient who has visceral disease at baseline and while on study has a CT or MRI brain ordered which reveals metastases. The patient's brain metastases are considered to be evidence of PD even if he/she did not have brain imaging at baseline.

If a new lesion is equivocal, for example because of its small size, continued therapy and follow-up evaluation will clarify if it represents truly new disease. If repeat scans confirm there is definitely a new lesion, then progression should be declared using the date of the initial scan.

## **2.3 Evaluation of Best Overall Response**

The best overall response is the best response recorded from the start of the study treatment until the end of treatment taking into account any requirement for confirmation. The patient's best overall response assignment will depend on the findings of both target and non-target disease and will also take into consideration the appearance of new lesions.

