## 4 STUDY DESIGN

### 4.1 Overall Study Design and Plan

[figure not shown]
This study is an open-label, Phase 1b/2 dose escalation and cohort expansion study designed to characterize the safety, tolerability, PK, pharmacodynamics, immunogenicity, and preliminary antitumor activity of MGD007 and MGA012, administered in combination by IV infusion, in patients with histologically proven, relapsed/refractory metastatic colorectal carcinoma, irrespective of the KRAS and MMR status of their tumors. This study will enroll patients as described below.

The study will proceed in 2 distinct phases as follows: Dose Escalation Phase to determine the MTD or MAD (if no MTD is defined) of the combination, followed by a Cohort Expansion Phase to further define the safety and initial antitumor activity of the combination with the doses established in the Dose Escalation Phase.

Patients will be treated with MGD007 and MGA012 as shown in [Figure 11](#). MGD007 will be administered at the target dose for each assigned cohort as an IV infusion over 120 minutes, once weekly (QW), in 8-week treatment cycles. MGA012 will be administered at 3 mg/kg as an IV infusion over 60 minutes, once every 2 weeks (Q2W) beginning on Cycle 1 Day 15, and every 2 weeks thereafter. For each patient, administration of the first dose of MGA012 will occur 2 weeks after the first dosing of MGD007. The DLT evaluation period will last until Cycle 1 Day 42. Disease status will be evaluated on Cycle 1 Day 56 ( $\pm$  3 days) using CT and/or MRI as appropriate for the sites of disease, accompanied by physical examination, and will then be evaluated every 8 weeks while on study treatment. Although response assessment will be performed according to both conventional (RECIST 1.1 [\[Appendix 5\]](#)) and irRECIST ([Appendix 6](#)), patients will be managed according to irRECIST principles. This approach allows for limited treatment of patients beyond the initial radiographic documentation of disease progression, assuming that the Investigator feels that the patients are tolerating therapy adequately, that patients remain otherwise clinically stable despite this initial radiographic evidence of disease progression, and that the Investigator feels the patient may still derive benefit from continuation of therapy.

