For patients who are otherwise clinically stable, but have met conventional criteria for PD, therapy may be continued at the discretion of the Investigator pending confirmation of progression at the next scheduled tumor assessment. This approach allows for limited treatment of patients beyond the initial radiographic documentation of disease progression, assuming that patients are tolerating therapy adequately, that patients remain otherwise clinically stable despite this initial radiographic evidence of disease progression and that the Investigator feels the patient may still derive benefit from continuation of therapy. Treatment of patients according to irRECIST principles is supported by well-documented evidence that in some patients treated with T-cell directed, immune-modulatory agents, tumors can evolve

to an objective response after an initial period, characterized by either apparent radiographic growth of target lesions or the development of new target lesions that would otherwise meet the criteria for disease progression using conventional response criteria.

For patients in whom progression is confirmed at the next scheduled tumor assessment, the criteria for irPD will have been met, and treatment with MGD007 and MGA012 should be discontinued. The patient should be removed from study participation after completion of the Post-treatment Follow-up period (see [Section 9.12](#)). However, for individual patients who meet these criteria, but who are otherwise considered to be experiencing clinical benefit in the judgment of the Investigator, consideration may be given to continue treatment with the MGD007 and MGA012 combination, on a case-by-case basis, in consultation with the Sponsor; see [Section 5.4](#).

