## 14.6 Efficacy and Endpoint Analyses

### 14.6.1 Response Endpoints and Analyses

For RECIST v1.1, the best overall response (BOR) will be categorized as CR, PR, SD, PD, or NE. To be qualified as BOR, CR and PR require confirmation at least 4 weeks after initial observation of such response, and SD requires to be observed at least once after 8 weeks (minus 3 days) from the start of MGD007 treatment.

For irRECIST, the best overall response (BOR) will be categorized as irCR, irPR, irSD, irPD, or irNE. To be qualified as BOR, irCR, irPR, and irPD require confirmation at least 4 weeks after initial observation of such response, and irSD requires to be observed at least once after 8 weeks (minus 3 days) from the start of MGD007 treatment.

The objective response rate (ORR) per RECIST v1.1 is estimated as the proportion of patients in response evaluable population who achieve BOR of CR or PR. Disease control rate is calculated as the proportion of patients who achieve a CR, PR, or SD. Progression-free

survival rate at 16 weeks will be calculated as the probability that patients are free of disease progression and alive at 16 weeks after the first dose of MGD007 by Kaplan-Meier method described below, based on response evaluable population and safety population, respectively. The 2-sided 95% exact binomial CI of the response rates will be calculated. The response rates per irRECIST will be estimated similarly. Subgroup analyses of these response rates by KRAS gene type (wild and mutant) and by MMR status (MSS and MSI-H) will be performed.

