### 2.3.3 Best Overall Response: All Time Points

The *best overall response* is determined once all the data for the patient is known.

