5 ENDPOINTS

5.1 Efficacy Endpoints

5.1.1 Response Endpoints

- Response by RECIST v1.1: The best overall response (BOR) will be categorized as CR, PR, SD, PD, or NE. To be qualified as BOR, CR and PR require confirmation at least 4 weeks after initial observation of such response, and SD requires to be observed at least once after 8 weeks (minus 3 days) from the start of MGD007 treatment.
- Immune related Response by irRECIST: The best overall response (BOR) will be categorized as irCR, irPR, irSD, irPD, or irNE. To be qualified as BOR, irCR, irPR, and irPD require confirmation at least 4 weeks after initial observation of such response, and irSD requires to be observed at least once after 8 weeks (minus 3 days) from the start of MGD007 treatment.

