5.1.2 Time to Event Endpoints

- Progression-free survival (PFS): The PFS is defined as the time from the first dose date of MGD007 to the date of first documented progression or death from any cause, whichever occurs first. For patients who are not known to be dead or progressed at the time of data cut-off for PFS analysis, the PFS will be censored at the date of the last tumor assessment. The documented progression is determined by radiographic assessment using RECIST v1.1. PFS will be calculated as:

$$\text{PFS (months)} = (\text{date of event [documented progression or death] or date of censoring} - \text{first dose date} + 1) / (365.25/12)$$

- Immune related PFS (irPFS): The irPFS is defined as the time from the first dose date of MGD007 to the date of first documented immune related progression (irPD) or death from any cause, whichever occurs first. For patients who are not known to be dead or progressed at the time of data cut-off for irPFS analysis, the irPFS will be censored at the date of the last tumor assessment. The documented irPD is determined by radiographic assessment using irRECIST. The irPFS will be calculated as:

$$\text{irPFS (months)} = (\text{date of event [documented immune related progression or death] or date of censoring} - \text{first dose date} + 1) / (365.25/12)$$

- Duration of response (DoR): The DoR is defined as the time from the date of initial response (CR or PR) to the date of first documented progression or death from any cause, whichever occurs first. The DoR is calculated only for the responders. For responders who are not known to be dead or progressed at the time of data cut-off for DoR analysis, the DoR will be censored at the date of the last tumor assessment. The documented progression is determined by radiographic assessment using RECIST v1.1. DoR will be calculated as:

$$\text{DoR (months)} = (\text{date of event [documented progression or death] or date of censoring} - \text{date of initial response} + 1) / (365.25/12)$$

DoR may also be determined by irRECIST.

- Overall survival (OS): The OS is defined as the time from the first dose date of MGD007 to the date of death from any cause. For patients who are not known to be dead at the time of data cut-off for OS analysis, the OS will be censored at the time they are last known to be alive. OS will be calculated as:

$$\text{OS (months)} = (\text{date of death or last known alive} - \text{first dose date} + 1) / (365.25/12)$$

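### RECIST 1.1 best overall response runs to end of treatment although treatment may continue past RECIST progression, so a confirmed PR reached after progression would count in the primary RECIST ORR

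*Protocol*

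**What the plan says.** Appendix 5 section 2.3 sets the RECIST 1.1 window: "The best overall response is the best response recorded from the start of the study treatment until the end of treatment", subject to any confirmation requirement. Section 2.3.3 adds that best overall response (BOR) "is determined once all the data for the patient is known".

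The statistical sections add two conditions, the same in both documents. Protocol 14.6.1 says: "To be qualified as BOR, CR and PR require confirmation at least 4 weeks after initial observation of such response". SAP 5.1.1 says: "SD requires to be observed at least once after 8 weeks (minus 3 days) from the start of MGD007 treatment". SAP 6.6.1 computes ORR and DCR from that BOR and sets no further limit on which assessments count.

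Treatment need not stop at RECIST progression, because patients are managed by irRECIST. Protocol 4.1 says: "This approach allows for limited treatment of patients beyond the initial radiographic documentation of disease progression". Protocol 11.1.1 says: "For patients who are otherwise clinically stable, but have met conventional criteria for PD, therapy may be continued at the discretion of the Investigator". This lasts until the next scan shows whether the progression is confirmed. The section gives as its reason that disease in some patients may move on, in its words, "to an objective response after an initial period, characterized by either apparent radiographic growth of target lesions or the development of new target lesions".

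Protocol 3.2.1 makes ORR, DCR and the 16-week PFS rate the primary measures of the expansion phase, using both RECIST 1.1 and irRECIST. Under Protocol 14.6.3 and SAP 5.1.2, PFS ends at first documented progression or death.

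**The concern.** An end-of-treatment window does no harm when treatment stops at progression, since hardly any later scan can enter it. Here the two are separated by design. A patient can have RECIST PD, stay on treatment, and have further scans inside the RECIST 1.1 BOR window.

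The conventional ORR could then include responses that appear only after conventional progression, which is the pattern irRECIST is there to capture. Appendix 6 section 2.4 uses the same window for irRECIST. For target-lesion growth that reverses, the two criteria would therefore give the same best response, and reporting both would show no difference in those patients. The same patient could also be a responder for RECIST ORR and a failure for RECIST PFS at 16 weeks, two primary measures of the same phase.

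**Working it through.** **1. Is there a stop at first RECIST PD?**
- Appendix 5 sections 2.3 and 2.3.3: the window ends at end of treatment, and all the patient's data are used.
- Table A-2: it covers a response followed by PD. It has no row that begins with PD, so it gives no rule for PD followed by response.
- The Appendix 5 note on continuing treatment to the next scan concerns equivocal findings, not a measured increase of 20% or more.
- Protocol 14.6.1, SAP 5.1.1 and SAP 6.6.1: confirmation for CR and PR, and a minimum time for SD. Nothing requires either to precede progression.

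No stop is stated.

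**2. Which progressions can be followed by a counted response?** Table A-1 assigns PD at any time point with a new lesion. A new lesion that persists therefore keeps later time points at PD. The gap is left for target or non-target growth that reverses and for a new lesion that resolves. PR is measured against the baseline sum (Appendix 5 section 2.2.1), so it stays reachable after PD in target lesions.

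**3. Worked case for ORR** (illustrative sums, scans on the protocol schedule, no new lesion, non-target disease not progressing). PD needs at least 20% and 5 mm over the smallest sum. PR needs at least 30% below baseline.

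| Scan | Sum (mm) | Change | Status |
|---|---|---|---|
| Baseline | 50 | | |
| Day 56 | 62 | 12/50 = +24%, +12 mm | PD |
| Day 112 | 34 | -16/50 = -32% | PR |
| Day 168 | 33 | -17/50 = -34% | PR |

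Day 168 is 56 days after Day 112, so the 4-week confirmation is met and RECIST 1.1 BOR is PR. By the SAP formula, RECIST PFS is an event at 56/(365.25/12) = 56/30.4375 = 1.84 months, before 16 weeks.

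**4. Worked case for DCR.** Baseline 50, Day 56 62 (PD), Day 112 55. The last is 5/50 = +10% over the smallest sum, hence SD at a scan more than 8 weeks from the start. Under Protocol 14.6.1 and SAP 5.1.1 taken alone, BOR is SD. Appendix 5 section 2.4.3, however, counts stable disease from treatment start only until progression criteria are met, which would deny this patient an SD period beyond Day 56. The passages do not agree.

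**5. Size.** The plan's own table first. The exact 95% limits for x of n are the 2.5% quantile of Beta(x, n-x+1) and the 97.5% quantile of Beta(x+1, n-x). With n = 25 and x = 2 to 7, all six rows of Protocol Table 13 (SAP Table 1) are reproduced to 0.1 point. The table is correct and is not affected by this point.

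One patient is 1/25 = 4 percentage points. The documents do not say how many patients would respond after PD. I assume 0 to 2 of 25 and, for illustration, 3 responders counted under the present wording:

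| Post-PD responders among the 3 | ORR if BOR stops at first RECIST PD | Exact 95% CI |
|---|---|---|
| 0 | 3/25 = 12% | 2.5 to 31.2 |
| 1 | 2/25 = 8% | 1.0 to 26.0 |
| 2 | 1/25 = 4% | 0.1 to 20.4 |

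**The case against.** Much can be said against a broad version of this point.

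- **Frequency.** Protocol 11.1.1 says only that the pattern can occur in some patients. The earlier MGD007 study (Protocol 2.3.4) lists 2 partial responses in 59, one unconfirmed, and describes none after progression. About 90% of the expansion cohort is expected to be MSS. A reader might infer that RECIST ORR will be inflated, but that follows only if such patients arise, and zero is a plausible number.
- **Half the cohort at risk.** A reader might scale the 30 of 59 with PD as best response to 25 patients (30/59 x 25 = 12.7). The documents do not support this. Those 30 may include patients judged on clinical progression without a scan, progression by a persisting new lesion stays PD, and continued treatment is limited to stable, tolerating patients at the investigator's discretion.
- **Negative duration of response.** SAP 5.1.2 says: "The DoR is defined as the time from the date of initial response (CR or PR) to the date of first documented progression". Taking that as the Day 56 event used for PFS gives (56 - 112 + 1)/30.4375 = -1.81 months in the worked case. This is a strained reading. Appendix 5 section 2.4.2 measures duration from the time response criteria are met until progression, which ordinarily means progression after the response.
- **DCR.** Appendix 5 section 2.4.3 gives a real argument that stable disease after PD would not count.
- **Unseen detail and stakes.** The separate statistical programming plan may contain a cut-off. The SAP calls the study primarily observational, the sample size rests on preliminary estimation, and no ORR threshold or test depends on the figure.

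These objections limit the size and reach of the point. They do not supply a stop for PR after reversible progression. The definition of a primary measure belongs in the protocol and SAP, whatever the programming plan contains.

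**Conclusion.** The point holds in limited form. As written, a confirmed PR reached after RECIST PD counts in the primary RECIST 1.1 ORR when the progression was target or non-target growth that reverses, or a new lesion that resolves. The same patient is an earlier RECIST PFS event. For DCR the wording is unresolved, not clearly wrong.

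Each affected patient moves ORR by 4 points, assuming 25 response-evaluable patients. Under the assumed 0 to 2 such patients, the shift is 0 to 8 points. That is small beside intervals more than 20 points wide, but it could change how a low response rate is read. Nothing here shows that such patients will occur, that a large share of the cohort is exposed, or that durations of response will be negative. The wording should be corrected before analysis, and no hypothesis test is at risk.

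**What to change.** In Appendix 5 section 2.3, Protocol 14.6.1 and SAP 5.1.1, state that RECIST 1.1 BOR uses assessments up to and including the first documented RECIST 1.1 PD, and that responses or stable disease seen only after that PD are reported under irRECIST. This also settles the conflict between the SD rule in Protocol 14.6.1 and SAP 5.1.1 and Appendix 5 section 2.4.3.

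With that cut, a RECIST response cannot follow RECIST progression. The RECIST DoR event is then the first progression after the response and cannot precede it. One clause in SAP 5.1.2 can say so.

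The cost is wording only, with no new scans or data and no change to patient management or sample size. The one downside is that RECIST 1.1 ORR and DCR may come out slightly less favourable. The late responses remain visible in the irRECIST results.
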